(Gardasil) in women. We will work within selected regions in Costa Rica and invite girls 9-14 years old (N=between 520 and 620; N=between 173 and 206 9-10 years and N=between 347 and 414 11-14 years) and women 18-25 years old (N=between 520 and 620) to visit dedicated study clinics. Randomization will not be utilized in this trial because age indicates vaccine product and number of doses. Therefore, vaccine product blinding is not necessary. Girls will be invited with their parents/legal guardians. At the first (baseline) study visit, the study will be described in detail. Written informed consent will be obtained from adult participants and parents/legal guardians of minor participants. Written assent will be obtained from girls 12-14 years old; girls younger than 12 will be provided with a study information document and their verbal agreement to participate will be recorded in the study management system.

The potential participant's medical history will be assessed by a clinician, including previous HPV vaccination. If needed for eligibility determination and at the clinician's discretion, the clinician can perform a physical examination to confirm good general health. If the potential participant is deemed potentially eligible, she will undergo blood collection. Participants 12 and older will be required to have a negative urine-based pregnancy test prior to vaccination, and sexually active participants will be instructed to use effective birth control methods (including abstinence) for 60 days after the last vaccination.

The initial vaccination will be administered at this baseline study visit; this will be either the first dose of Gardasil or the single dose of Cervarix. Participants will be monitored for adverse events at the clinic for 15 minutes following vaccination. Appropriate medical treatment will be readily available in the rare event that an anaphylactic reaction develops. A real-time contact service (such as a toll-free number or text messaging system) will be staffed for the duration of the trial so that participants may contact the trial's clinical team in case of study-related medical concerns or questions.

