Among women scheduled to receive Gardasil, the second and third vaccine visit will occur two and six months following the initial baseline visit. Qualified staff and clinicians will conduct these study visits. After a negative urine-based pregnancy test, the visit will conclude with vaccination and monitoring for adverse events. All adverse events, serious and not serious, will be documented.

All participants will have blood collected at the 12, 24, and 36 month follow-up visits, either in a clinic or home setting (Table 2). For participants in the Cervarix group, blood also will be collected at a follow-up visit one month after vaccination. Each girl is expected to have five study visits, one for vaccination and four follow-up visits. Each woman is expected to have six study visits, three for vaccination and three for follow-up.

Table 2. Proposed study visits for the two groups.

	Visit type (months)						
Age	V00*	V01	V02*	V06*	V12	V24	V36
9-14 years	X	X			X	X	X
18-25 years	X		X	X	X	X	X

*Indicates vaccination visit

Throughout the duration of the trial, we will monitor plans for country-wide implementation of HPV vaccination, which will target fourth-grade girls (usually 10 year olds). At the time when the country begins vaccination, we will initiate procedures for ceasing enrollment of 9- and 10-year olds according to the SOP requested by the DSMB. Note, our recruitment plan for the younger cohort ensures that we will include 347 girls that will not be targeted by the national vaccination program.

Finally, if at 36-months the GMT for 1 dose at the group level is inferior to that of 3 doses, all 1-dose girls will be invited to receive the 2nd dose of Cervarix.

Selection of Study Vaccines

Both vaccines to be used in this study are licensed in the US and Costa Rica. As described, the bivalent HPV vaccine is produced by GSK (Cervarix®) and contains HPV 16 and 18 antigens, the quadrivalent vaccines is produced by Merck (Gardasil®) and additionally contain HPV 6 and 11 antigens. Besides the differences in HPV types included, the bivalent vaccine has a proprietary adjuvant called AS04, consisting of monophosphoryl lipid A (MPL) and aluminum hydroxide. MPL is a detoxified bacterial lipopolysaccharide which is a TLR-4 agonist involved in activation of innate and adaptive immune responses. The quadrivalent vaccine has aluminum hydrophosphate sulfate as adjuvant.

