Because the national vaccination program has been initiated, there is the potential that some girls enrolled at ages 9-10 years may have received an additional vaccination dose but have failed to report it. Therefore, we plan to conduct the following secondary/sensitivity analysis. We will compare GMTs, distributions, and seroconversion rates for HPV-16 and HPV-18 antibodies, assessed at 24 and 36 months after initial vaccination, between 11-14 year old girls receiving 1 dose of Cervarix and 18-25 year old women receiving 3 doses of Gardasil. We will also calculate the GMT ratios, comparing girls 9-10 years old at vaccination with girls 11-14 years old at vaccination, and their 95% confidence intervals for HPV-16 and HPV-18 antibody levels at 1 month and 1-year post-vaccination. Additionally, we will test for HPV6/HPV11 antibodies in a subset of participants who are at-risk for external HPV vaccination or show serologic evidence of additional HPV vaccine doses.

Power and Sample Size Considerations

We calculate the power to show non-inferiority at 24 months and the power to show non-inferiority at 36 months given that we enroll 520 women 18-25 year old and 347 girls 9-14 year old. Specifically, we assume that $\hat{\sigma} = 1.38$, 20% of all 18-25 year old women do not receive all 3 doses, 100% of 9-10 year old girls (i.e. worst case scenario) receive a vaccination outside the study, 20% of all participants are lost-to-follow up, 10% of the 18-25 year old women are seropositive at baseline, 5% of the 11-14 year old girls are seropositive at baseline, the common true ratio, R, for HPV-16 and HPV-18 is 1, and the non-inferiority threshold (t) is 0.67, in accordance with the recommendation of the WHO Expert Committee on Biological Standardization(60). Based on these assumptions, we will have 65% power to demonstrate non-inferiority at 24 months and 84% power to demonstrate non-inferiority at 36 months. Power calculations for other values of R and t are listed in table 4. Note the power reported for 36 months is $\Pr(\min(\hat{R}_{0.02}^{16}(36), \hat{R}_{0.02}^{18}(36)) > t)$, a lower bound for the probability of rejecting non-inferiority at either the 24- or 36- month analysis. In the more optimistic scenario, where 9-10 year old participants do not receive vaccinations outside the study, our power increases to 78% at 24 months and 91% at 36 months.

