For the potential secondary analysis, we would calculate the GMT ratios, comparing girls 9-10 years old at vaccination with girls 11-14 years old at vaccination, and their 95% confidence intervals for HPV-16 and HPV-18 antibody levels at 1 month and 1 year post-vaccination. Assuming that enrollment includes 173 girls 9-10 years old and 347 girls 11-14 years old, 5% of all girls are seropositive at baseline, 10% of all girls do not return for the 1 month visit, $R = 1$, and $\hat{\sigma} = 1.38$, the expected length of the 95% confidence interval for $\hat{R}^H(1)$ is 0.55 (i.e. if $\hat{R}^H(1) = 1$, the expected 95% confidence interval would be 0.76 – 1.31).

Table 4: Power calculations. The table lists the power to demonstrate non-inferiority at the 24- and 36-month analyses for a non-inferiority threshold of 0.67 and three values of the common true ratio (R=0.8, 1.0, 1.2), with other parameters set at the values described in the text.

Threshold = 0.67		
	Power (24 months)	Power (36 months)
R = 0.8	0.02	0.09
R = 1.0	0.65	0.84
R = 1.2	>0.99	>0.99

HUMAN SUBJECTS PROTECTIONS

This trial will be conducted in compliance with regulations for human subject research in effect in Costa Rica (Costa Rican Human Research Law 9234) and the United States (The Belmont Report & Title 45 Code of Federal Regulations, Part 46, Protection of Human Subjects, and Declaration of Helsinki). The principles of respect for persons, beneficence, and justice will be paramount in planning our trial with all the necessary considerations related to inclusion of minors.

In addition to specialized training associated with their roles, all study staff involved in study interactions with participants, their confidential data or samples (e.g., outreach workers, clinic staff, relevant systems staff, laboratory staff, sub-investigators and principal investigators), will complete GCP training in accordance with the requirements of the Costa Rican Ministry of Health, which authorizes them to conduct human research. They will sign a confidentiality agreement as part of their contract.

Institutional Approvals

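### The power section gives the wrong age range for its 347 girls (they are the 11-14 stratum, not 9-14), and one Table 4 cell is slightly overstated; the base-case powers stand

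*Protocol*

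**What the plan says.** The first paragraph of Power and Sample Size Considerations (protocol, Analysis Plan) computes power on the basis that "we enroll 520 women 18-25 year old and 347 girls 9-14 year old". Among its assumptions are that "20% of all 18-25 year old women do not receive all 3 doses" and that "100% of 9-10 year old girls (i.e. worst case scenario) receive a vaccination outside the study". It reports 65% power at 24 months and 84% at 36 months when the true ratio R is 1. In a more optimistic scenario, where the 9-10 year olds are not vaccinated elsewhere, it reports 78% and 91%.

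Other places in the protocol attach 347 to a different age range:

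- The Overview under Study Design and Methods of Trial plans 520 to 620 girls aged 9-14, split as "N=between 173 and 206 9-10 years and N=between 347 and 414 11-14 years".
- The same Overview says "our recruitment plan for the younger cohort ensures that we will include 347 girls that will not be targeted by the national vaccination program". That programme targets girls of about 10.
- The next paragraph of the power section, on the secondary comparison of age groups, begins "Assuming that enrollment includes 173 girls 9-10 years old and 347 girls 11-14 years old".

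Of Table 4 the caption says: "The table lists the power to demonstrate non-inferiority at the 24- and 36-month analyses for a non-inferiority threshold of 0.67". The entries for 24 and 36 months are 0.02 and 0.09 at R = 0.8, 0.65 and 0.84 at R = 1.0, and above 0.99 in both columns at R = 1.2.

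The SAP has no power section, so this protocol section is the only statement of the basis for the primary power.

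**The concern.** Taken as written, the sentence makes 347 the whole enrolment of girls. Two things then fail to fit. The same paragraph removes every 9-10 year old, since girls vaccinated outside the study leave the According to Protocol cohort, so 347 would have to be cut again. And the optimistic scenario needs the 9-10 year olds as additional girls, whom the sentence leaves out.

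At stake is whether the primary power can be reproduced from its stated basis. The protocol hopes to support a label change, and an assessor checking the power will begin with this sentence. The Table 4 question is smaller: whether every cell describes the same event, namely success for both HPV types.

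**Working it through.** **Inputs** (power section unless noted)

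- Women: 520 enrolled; 20% do not complete three doses, 20% are lost to follow-up, 10% are seropositive at baseline.
- Girls: 347 enrolled; 20% are lost to follow-up, 5% are seropositive at baseline (a rate given for ages 11-14).
- SD of log antibody 1.38; threshold 0.67.
- Two-sided 99% interval at 24 months (z = 2.576) and 96% at 36 months (z = 2.054), from the Analysis section.
- Success requires both HPV types to pass. The power section defines its 36-month figure through the minimum of the two lower limits.

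**Method.** Normal approximation on the log scale:

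- SE = 1.38 × √(1/n women + 1/n girls)
- power for one type = Φ[(ln R − ln 0.67)/SE − z]
- joint power = (power for one type)², treating the two types as independent

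The protocol does not state the independence or the multiplicative attrition. They are used because they reproduce its figures. Adding the attrition rates instead gives 59% and 80% at R = 1, which does not match.

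**Step 1: reproduce the base case with 347 girls aged 11-14**

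- Women: 520 × 0.8 × 0.8 × 0.9 = 299.5
- Girls: 347 × 0.8 × 0.95 = 263.7
- SE = 1.38 × √(1/299.5 + 1/263.7) = 0.1165
- At R = 1, −ln 0.67 = 0.4005 and 0.4005/0.1165 = 3.44
- 24 months: Φ(3.44 − 2.576) = 0.805; squared, 0.649 (stated 65%)
- 36 months: Φ(3.44 − 2.054) = 0.917; squared, 0.840 (stated 84%)

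**Step 2: the age range of the 347**

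The secondary calculation uses 173 girls aged 9-10 and 347 aged 11-14, with 5% seropositive and 10% missing the 1-month visit. The evaluable numbers are 173 × 0.95 × 0.9 = 147.9 and 347 × 0.95 × 0.9 = 296.7. The SE is 1.38 × √(1/147.9 + 1/296.7) = 0.139, and the interval is exp(±1.96 × 0.139) = 0.76 to 1.31, length 0.55, as stated. So 347 means ages 11-14 there too.

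**Step 3: Table 4 by the same method (SE 0.1165)**

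| R | 24 months, computed | 24 months, stated | 36 months, computed | 36 months, stated |
|---|---|---|---|---|
| 0.8 | 0.021 | 0.02 | 0.088 | 0.09 |
| 1.0 | 0.649 | 0.65 | 0.840 | 0.84 |
| 1.2 | 0.985 | >0.99 | 0.997 | >0.99 |

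For R = 1.2 at 24 months, ln(1.2/0.67) = 0.5828; 0.5828/0.1165 = 5.00; Φ(5.00 − 2.576) = 0.9924; squared, 0.985. If the two types are correlated, the joint value is 0.985 at correlation 0.3 and 0.989 at 0.9, still below 0.99. The single-type value, 0.992, is above 0.99, but the documents do not say how the cell was obtained.

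**The case against.** The strongest reply is that nothing of substance is wrong. The figures of 65% and 84% follow almost exactly from the planned 520 women and 347 girls aged 11-14. The paragraph itself says that the 9-10 year olds are removed as a worst case, and it gives the girls' seropositivity rate for ages 11-14. A careful reader can therefore work out which girls are counted, and it would be unfair to say that the text hides this. The Table 4 gap is about half a percentage point, in a favourable scenario at the interim look. All of this stands, and it is why the point is minor. It does not make the sentence right, and the value above 0.99 is not recovered at any between-type correlation tried.

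Two stronger readings are tempting and should not be drawn.

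- **That the true power is about 47% and 71%.** A reader might take 347 as all girls aged 9-14 and remove the 9-10 share. With that share assumed to be 173/520, the evaluable girls are 347 × (347/520) × 0.8 × 0.95 = 176.0, the SE is 0.1311, and the powers are 0.468 and 0.709. But the Overview sets the 9-14 total at 520 to 620, so nobody proposes this design.
- **That 78% and 91% are also wrong.** With 520 girls, 520 × 0.8 × 0.95 = 395.2 are evaluable, the SE is 0.1057, and the powers are 0.787 and 0.919. The power paragraph gives no seropositivity rate for ages 9-10; the 5% used here for all girls is borrowed from the secondary calculation. A gap of about one point under a borrowed input, which truncation would also explain, does not show an error.

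**Conclusion.** Wrong as written, minor. The sentence that gives the basis for the primary power carries the wrong age range: 347 is the minimum aged 11-14, and 520 is the minimum aged 9-14. The effect on the base-case power is nil, because 65% and 84% reproduce as 0.649 and 0.840. It would be wrong to conclude that the stated powers do not follow from the design. They do; they just do not follow from that sentence.

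The Table 4 cell for R = 1.2 at 24 months should be about 0.985 (0.985 to 0.989 for between-type correlations of 0 to 0.9) rather than above 0.99. This rests on the normal approximation and multiplicative attrition. Independence of the two types matters little for this cell, but it is what reproduces the R = 0.8 and R = 1.0 rows. No decision depends on the cell.

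**What to change.** In the protocol's power section:

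1. Give the enrolment as 520 women aged 18-25 and 520 girls aged 9-14, of whom 347 are aged 11-14.
2. Say that 65% and 84% are the worst-case powers, resting on those 347 girls alone.
3. In Table 4, change the entry for R = 1.2 at 24 months to 0.98.

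Leave 78% and 91% as they are. The cost is a text correction, with one table entry slightly less favourable. Enrolment, margin, confidence levels, analysis and base-case power are unaffected.

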27 March 2019	Version 1.3: Revisions to the methods, analysis plan, and procedures related to a new follow-up visit one month post-vaccination to collect blood from the Cervarix group (girls ages 9-14). This change was recommended by the CVT Working Group as a means to bridge the 9-10 year olds to the 11-14 year olds in the event that initiation of HPV vaccination in fourth graders, as part of the National Immunization Program, requires exclusion of the 9-10 year olds from the primary analysis. Corresponding modifications also were made to the forms and videos for assent and parental consent, and the information form. The new re-assent form for participants who turn 12 during follow-up was also included, as was the new invitation PowerPoint for recruitment.
22 May 2019	Version 1.4: Revisions to the objectives, overview, and analysis plan requested by the EMA, a clarification to the content regarding the field response to the national vaccine program, and a change in the exclusion criteria to remove latex, and an increase in the accrual ceiling to permit the enrollment of up to 100 additional participants per study group.
7 July 2022	Version 1.5: Revisions to the analysis plan to incorporate evolving knowledge about the impact of the national vaccine program, and changes to reflect that NCI ethical oversight will be conducted by an ethics review panel, no longer the NCI IRB.
3 March 2023	Version 1.6: Revisions to the analysis plan to add HPV6/11 testing of selected participants and move SEAP testing to 36-month visit.

**Statistical Analysis Plan to Address the Primary and Secondary Objectives for the Trial
Entitled**

“Non-inferiority trial comparing immunogenicity from 1-dose of bivalent HPV vaccine in girls to 3-doses of quadrivalent vaccine in women: The PRIMAVERA-ESCUUDO Trial (‘Puente de Respuesta Inmunológica para Mejorar el Acceso a Vacunas y Erradicar el cancer’)”

(NCI Protocol 19-C-009)

Date: February 28, 2023

ClinicalTrials.gov ID: NCT03728881

Table of Contents

1. Introduction	3
2. Objectives	3
2a. Primary Objective	3
2b. Secondary Objectives	3
3. Analytical Cohorts	4
3a. Primary Analytical Cohort	4
3b. Secondary/Exploratory Analytical Cohorts	4
4. Endpoints	5
5. Implementation of Analysis	5
6. Controlling the Type-I error rate	5
7. Statistical Analyses for Immunogenicity	5
7a. Methods for The Primary Objective	5
7b. Methods for The Secondary Objectives	6
7c. Methods for Sensitivity and Exploratory Analyses	6
8. Statistical Analyses for Evaluating ELISA assays	7

1. Introduction

This document describes the pre-planned analysis for the trial entitled “**Non-inferiority trial comparing immunogenicity from 1-dose of bivalent HPV vaccine in girls to 3-doses of quadrivalent vaccine in women**”.

2. Objectives

2a. Primary Objective

Primary Objective (PO): To demonstrate that the immunogenicity (as determined by ELISA) of a single dose of Cervarix in 9-14 year old girls is non-inferior to the immunogenicity of three doses of Gardasil, administered at 0, 2, and 6 months, in 18-25 year old women 36 months after initial vaccination, with an interim analysis at 24 months after initial vaccination.

Either of following criteria will qualify as non-inferiority:

- The interim analysis will assess non-inferiority at 24 months. Non-inferiority will be demonstrated if the lower limits for the two-sided 99% confidence intervals of the GMT ratios (1-Dose Cervarix divided by 3-Doses of Gardasil at 24 months) for both HPV-16 and HPV-18 antibody levels exceed 0.67.
- The primary analysis will assess non-inferiority at 36 months. Non-inferiority will be demonstrated if the lower limits for the two-sided 96% confidence intervals of the GMT ratios (1-Dose Cervarix divided by 3-Doses of Gardasil at 36 months) for both HPV-16 and HPV-18 antibody levels exceed 0.67.

2b. Secondary Objectives

Secondary Objective 1 (SO1): To compare the distribution of both HPV-16 and HPV-18 antibodies levels, assessed at 24 and 36 months after initial vaccination, following a single dose of Cervarix in 9-14 year old girls and following three doses of Gardasil, administered at 0, 2, and 6 months, in 18-25 year old women.

Secondary Objective 2 (SO2): To compare rates of seroconversion based on both HPV-16 and HPV-18 antibody levels, assessed at 24 and 36 months after initial vaccination, following a single dose of Cervarix in 9-14 year old girls and following three doses of Gardasil, administered at 0, 2, and 6 months, in 18-25 year old women.

Secondary Objective 3 (SO3): To compare GMTs, distributions, and seroconversion rates for HPV-16 and HPV-18 antibodies, assessed at 24 and 36 months after initial vaccination, following a single dose of Cervarix in 11-14 year old girls and following three doses of Gardasil, administered at 0, 2, and 6 months, in 18-25 year old women.

Secondary Objective 4 (SO4): To compare GMTs, distributions, and seroconversion rates for HPV-16 and HPV-18 antibodies, assessed at 1-month and 1-year after vaccination, following a single dose of Cervarix in 9-10 year old girls and following a single dose of Cervarix in 11-14 year old girls.

Secondary Objective 5 (SO5): To evaluate whether baseline variables (i.e. age, enrollment date, district) are associated with GMTs, distributions, and seroconversion rates for HPV-16 and HPV-18 antibodies, assessed at 24 and 36 months after initial vaccination.

We note that SO3 and SO4 are, in part, included in this study because of Costa Rica's national vaccination program that aimed to vaccinate 10-year-old girls starting in 2019.

3. Analytical Cohorts

3a. Primary Analytical Cohort

The According to Protocol (ATP) cohort for a specified HPV type (i.e. HPV 16 or HPV 18) and timing (i.e. 24-month or 36-month) are the participants who satisfy the following set of requirements:

- Received the correct number of doses within the predefined vaccination windows. Denoting T_1 as the time of the first vaccination, the window for the second vaccination is between T_1+30 days and T_1+90 days. Denoting T_2 as the time of the second vaccination, the window for the third vaccination is between T_2+90 days and T_1+360 days.
- Not seropositive at baseline for the specified HPV type.
- Blood collected within the predefined follow-up window. Denoting T_1 as the time of the first vaccination, the window for the 24-month visit is between T_1+700 days and T_1+912 days and the window for the 36-month window is T_1+1065 days and T_1+1278 days.
- No HPV vaccination outside of the study prior to blood collection. The participant did not report receiving an HPV vaccine and, among those tested, did not have HPV6 and HPV11 vaccine-level antibodies.

Note, the ATP cohort for a given analysis depends on both the timing of the analysis and the specified HPV type.

3b. Secondary/Exploratory Analytical Cohorts

We will also consider the: (i) modified Intention-to-Treat (ITT) cohort, including all participants receiving the correct number of doses and with blood collected during the predefined follow-up window; (ii) Seropositive-ATP (SP-ATP) cohort that includes participants who are seropositive at baseline, but otherwise satisfy the ATP requirements; and (iii) Serocombined-ATP (SC-ATP) cohort that combines the ATP and SP-ATP cohorts. Furthermore, for SO4, we will consider all

girls who are not seropositive at baseline, had blood collected between $T_1 + 14$ and $T_1 + 90$ days for the 1 month analysis and between $T_1 + 274$ and $T_1 + 547$ days for the 1 year analysis, and did not receive an HPV vaccination outside of the study prior to their blood collection. Additionally, we will test for HPV6/HPV11 antibodies in a subset of participants who are at-risk for external HPV vaccination or show serologic evidence of additional HPV vaccine doses.

4. Endpoints

The four endpoints are HPV-16 and HPV-18 specific antibody results obtained from blood specimens (serum) collected at the 24- (interim) and 36-(primary) month visit (i.e. 4 endpoints = 2 HPV types x 2 time-points). All antibody levels are measured by HPV type-specific ELISA. Two additional endpoints, HPV-16 and HPV-18 antibody levels measured from serum collected at the 1-month visit and the 1-year visit, will also be included to achieve Secondary Objective 4 (SO4).

5. Implementation of Analysis

The final 24- and 36-months analyses will be performed once the corresponding follow-up window for the last enrolled participant closes

6. Controlling the Type-I error rate

The analysis defined in the following section ensures that under the null hypothesis of inferiority, the probability of declaring non-inferiority (i.e. type I error rate) is less than 0.025 for HPV-16 and HPV-18 endpoints, respectively.

7. Statistical Analyses for Immunogenicity

7a. Methods for The Primary Objective

We will estimate the GMT ratios for HPV-16 and HPV-18 at 24 and 36 months in the corresponding ATP cohort.

We define $R^H(t) = GMT_1^H(t)/GMT_3^H(t)$ to be the GMT ratio for HPV-H (i.e. HPV-16 or HPV-18) at time point t (i.e. 24 or 36 months) when comparing antibody levels in 9-14 year old girls receiving 1 dose of Cervarix to levels in 18-25 year old women receiving 3 doses of Gardasil.

We will estimate $R^H(t)$ by fitting a generalized estimating equation (GEE) model where the dependent variable is the log-antibody level and the independent variable is study-group. Denoting the estimated coefficient for study-group by $\hat{\beta}^H(t)$ and the corresponding robust standard error by $\hat{\sigma}^H(t)$, we define our estimate by $\hat{R}^H(t) = \exp(\hat{\beta}^H(t))$ and define the two-sided $(1-\alpha)\%$ confidence interval (CI), $(\hat{R}_{\alpha/2}^H(t), \hat{R}_{1-\alpha/2}^H(t))$, by $\exp(\hat{\beta}^H(t) \pm z_{1-\alpha/2} \hat{\sigma}^H(t))$, where $z_{1-\alpha/2}$ is the $1-\alpha/2$ quantile of a normal distribution. In the model, we will group girls into clusters of full siblings and use an exchangeable correlation matrix.

We will declare non-inferiority if $\min\left(\hat{R}_{0.005}^{16}(24), \hat{R}_{0.005}^{18}(24)\right) > 0.67$ or, upon failure of that criterion, $\min\left(\hat{R}_{0.02}^{16}(36), \hat{R}_{0.02}^{18}(36)\right) > 0.67$. Note, under the null hypothesis that both $\min(R^{16}(24), R^{18}(24)) < 0.67$ and $\min(R^{16}(36), R^{18}(36)) < 0.67$, the probability of declaring non-inferiority or the Type I error rate is less than 0.025.

7b. Methods for The Secondary Objectives

Secondary Objective 1 (SO1): For each combination of HPV-type, time-point, and study group, we will describe the distribution of antibody levels by showing the reverse cumulative distributions (i.e. 1-cumulative distribution function) in the ATP cohort.

Secondary Objective 2 (SO2): For each combination of HPV-type, time-point, and study group, we will report the proportion of the ATP cohort who seroconvert (i.e. achieve HPV-16 or HPV-18 antibody levels greater than 1.41 international units (IU)/mL or 1.05 IU/mL, respectively) and exact 95% confidence intervals. For each HPV-type and time-point, we will assess whether seroconversion rates differ between study groups using fisher's exact test.

Secondary Objective 3 (SO3): We will repeat the analyses described for the primary objective and secondary objectives 1 and 2 restricted to 11-14-year-old girls. We will also perform a direct comparison of the antibody levels in 9-10 and 11-14 year old girls (e.g. compare GMT in GEE w/ age group as the independent variable, compare seroconversion rates by fisher's exact test).

Secondary Objective 4 (SO4): We will repeat the analyses described for the primary objective and secondary objectives 1 and 2 to compare antibody levels at 1-month and 1-year post-vaccination in girls 9-10 years old girls and in girls 11-14 years old.

Secondary Objective 5 (SO5): We will consider the following baseline covariates: age, enrollment date, and district. Within each study-group and at each time point, we will report the GMTs and their 95% CIs for HPV-16 and HPV-18 antibody levels in subgroups defined by these baseline covariates. Moreover, we will use GEEs to assesses the association between GMTs and these baseline covariates and show both reverse cumulative distributions and seroconversion rates by subgroup.

7c. Methods for Sensitivity and Exploratory Analyses

We will repeat the methods for the primary and secondary objectives using the ITT, SP-ATP, and SC-ATP cohorts instead of the ATP cohort.

We will repeat the methods for the primary and secondary objectives after removing potential outliers (e.g. participants potentially exposed to a vaccination outside of study) where the antibody level is $2 \times \text{IQR}$ above the 75th percentile.

We will assess whether antibody levels are changing over time. For each combination of study group and HPV type, we will compare GMTs at 24 and 36 months.

8. Statistical Analyses for Evaluating ELISA assays And Comparability with SEAP-NA

HPV binding is measured by ELISA. The quantity of HPV16 and 18 IgG antibody response measured by VLP ELISA will be utilized to address immunogenicity endpoints. To further define the primary analytic cohort, HPV6 and HPV11 antibodies will be measured by VLP ELISA in a subset of participants to confirm, beyond self-report, that the according to protocol analytic cohort includes only girls who did not receive external HPV vaccination through the national program, which uses quadrivalent vaccine (HPV 6, 11, 16, 18). This will assure that girls in the single-dose HPV vaccination arm did not get additional doses.

HPV neutralization is measured by SEAP-NA. Antibodies levels measured by ELISA will be compared to neutralizing antibody levels measured by the pseudovirion-based neutralization assay, SEAP-NA. This nested study will select 24- month serum samples from a random set of 100 baseline seronegative 18-25 year old women and a random set of 100 baseline seronegative 9-14 year old girls, and then evaluate the HPV-16 and HPV-18 antibody levels in each of those 200 samples using both ELISA and SEAP-NA. For each HPV type, we will perform a Deming regression comparing $\log(\text{ELISA})$ levels with $\log(\text{SEAP})$ levels, where $\log(\text{ELISA})$ is the dependent variable and $\log(\text{SEAP})$ is the independent variable. We will confirm that ELISA is an acceptable assay for the primary endpoint if the 95% confidence intervals of the regression slope excludes $1-\Delta$ and $1+\Delta$ for both HPV types, with $\Delta = 0.3$. If that criterion is not achieved, then we will initiate a discussion with relevant parties to assess acceptability of the assay.
